4.1.4 Per Protocol Population

No per protocol population is planned for this study.

4.2 General Definitions

4.2.1 Study Periods

The time of a participant's participation in the study will be divided into three periods. The Screening Period refers to the time between signing of informed consent to the day prior to the day of the first treatment. Study Period 1 refers to the time between the day of the first treatment (Treatment 1) up to but not including the day of the second treatment (Treatment 2). Study Period 2 refers to the time between the day of the second treatment up to and including the 12-month visit, recognizing that for those who initially receive cellular therapy, Study Period 2 occurs post cellular therapy and therefore is not a true sham period.

4.2.2 Baseline

For all visits occurring during Study Period 1, baseline will be defined based on the measurements taken prior to Treatment 1 (during the screening/baseline visits). For all visits occurring during the Study Period 2, baseline will be defined based on the measurements taken during the Month 6 visit immediately prior to Treatment 2. It is noted that for participants in the sham/deferred treatment group, these two sets of baseline measurements should be similar due to the fact that no active treatment is given during the Study Period 1. We will review the values of these two sets of baseline measures to examine the extent to which this is true.

4.2.3 Adverse Event

An adverse event (AE) is any untoward medical occurrence, whether or not considered treatmentor procedure-related, which occurs during the conduct of the study. Medical conditions or diseases present before a participant has study treatment on Day 0 are only considered adverse events if they worsen after the participant has signed ICF (temporal association).

A suspected adverse reaction is any adverse event for which there is a reasonable possibility that the study treatment caused the adverse event. A reasonable possibility implies that there is evidence that the study treatment caused the event.

An adverse reaction is any adverse event caused by the study treatment.

4.2.4 Serious Adverse Event

A Serious Adverse Event (SAE) is defined as any adverse event that suggests a significant hazard, contraindication, side effect, or precaution. This includes, but may not be limited to any of the following events:

- 1. Death
- 2. Life-threatening (Life-threatening means that the study participant was, in the opinion of the investigator, at immediate risk of death from the reaction as it occurred.)
- 3. Persistent or significant incapacity or substantial disruption of the ability to conduct normal life functions
- 4. Inpatient hospitalization or prolongation of existing hospitalization
- 5. Congenital abnormality or birth defect
- 6. Important medical event that may not result in one of the above outcomes, but may jeopardize the health of the study participant or require medical or surgical intervention to prevent one of the outcomes listed in the above definition of serious event.
- 7. Vision-threatening (Refer to Section 8.3, Vision threatening Adverse Events)

Hospitalization or surgery for diagnostic or elective procedures for a preexisting condition is not considered an SAE. A pre-existing condition can be an SAE if the frequency, intensity, or character of the condition worsens after signing of informed consent. If any questions arise regarding what may qualify as an adverse event or SAE, the Medical Monitor at the DCC will be consulted.

Unexpected Event or Reaction: An event or reaction is considered "unexpected" when its nature (specificity) or severity is not consistent with applicable product information, such as safety information provided in the package insert, the investigational plan, or the investigator's brochure.

4.2.5 Post-treatment AEs

Post-treatment AEs are events that occur on or after the day of the first treatment (cellular or sham).

4.3 Tables, Figures and Listings Conventions

Safety analyses will be summarized for the safety population. All other analyses described in this document will be done for the ITT population and summarized by randomized treatment group and overall. For all summaries of ITT population, participants will be analyzed according to the treatment arm to which they were randomized regardless of the subsequent sequence of events regarding study drug exposure.

Continuous variables will be summarized using the following descriptive statistics: n (non-missing sample size), mean, standard deviation, percentiles (median, maximum, and minimum). Categorical variables will be summarized in terms of frequencies and/or percentages.

Any deviations from the above general conventions will be noted in the subsequent sub-sections.

5.0 STUDY POPULATION

Eligible participants include adult men and women having persistent vision loss due to CRVO with or without concurrent retinal artery occlusion in the study eye and meet all of the inclusion criteria and none of the exclusion criteria as outlined in the study protocol.

As this is a phase I/II study and the number of participants is small, all available data from participants who meet the protocol's eligibility criteria and who were not involved in any significant protocol violations will be used. The intent-to-treat population consists of all randomized participants who receive the first treatment.

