Protocol monitoring will be a continuous process performed both at the DCC and at the Enrollment Center. The DCC staff will be in regular communication with both Study Coordinators and the PI, via email or teleconference, at least monthly to discuss general study issues and to assure the site is up to date with data completion. At least monthly, data quality reviews will be conducted to assess level of missing data, review requests for missing values and missing forms exceptions, and run data checks for missing and inconsistent data. Any departure from procedures or requirements outlined in the protocol will be classified as protocol deviations. Prior to study initiation, a site initiation visit will be conducted by a DCC protocol monitor to ensure the site possesses adequate facilities and staffing to conduct the study, that site personnel have sufficient knowledge to ensure the study is conducted in accordance with GCP, applicable regulations, and the approved protocol, and that they are adequately trained in study policies and procedures. Interim monitoring visits will be conducted to monitor for informed consent documentation, protocol adherence, reporting of protocol deviations, study outcomes, participant safety, maintenance of appropriate source documentation and regulatory reviews. Protocol monitoring visits conducted by a DCC monitor will occur approximately every 6 months after enrollment begins. A site close-out visit will be conducted at the conclusion of the study. Complete and accurate regulatory documentation, complete data entry, and no pending action items are required before the site is closed out.

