4.1.2 Intent-to-Treat Population

The (modified) intent-to-treat population consists of all participants who were randomized and received the first injection (cellular or sham). For analyses, these participants will be analyzed in the arm to which they were randomized.

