7.3 Secondary Efficacy Outcomes

Availability of the secondary outcomes will first be summarized by treatment arm and visit. Due to each secondary outcome having numerous measures associated with it (e.g., the OCT outcome can be measured by looking at macular thickness (central, pericentral and/or peripheral), macular volume, average macular thickness, presence of CME and/or subretinal fluid, integrity of photoreceptor layer, etc.), outcome measures thought to be of most importance were chosen by the Study Chair prior to any knowledge of treatment assignment. Using this pre-selected list of outcome measures, the following strategy will be used to analyze each continuous outcome.

- 1. Summary table of **descriptive** statistics broken down by treatment arm, Treatment Period and visit for change from baseline in the outcome measure. For VA and microperimetry, the summary table will also include the outcome measure on the original scale.
- 2. Analysis of **treatment effect** of cellular vs sham therapy during Treatment Period 1 (as described in Section 7.3.1.1) for the outcome measure on the original scale and change from baseline.
- 3. Analysis of **effect of cellular treatment over time** (as described in Section 7.3.1.2) for the outcome measure on the original scale and change from baseline.

For those outcomes that are categorical, a summary table of counts and frequencies will be provided, with any other planned analyses described within the relevant section.

These analyses will be conducted to gauge any changes in the outcome measures that could be attributed to the cellular therapy and to differentiate these changes from non-treatment factors (i.e., natural course of the condition, learning or placebo effects or testing variations). Graphical measures will be used to summarize and display trends over time. A (modified) intent-to-treat approach will be followed in which all participants who were randomized *and received the first injection* (cellular or sham) will be included in the analysis and analyzed in the arm to which they were randomized.

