7.5 Methods for Handling Missing Data

As this is an exploratory phase I/II study, all available data will be used for all analyses. If the amount of missing data is >5% and there is reason to believe the data are not missing completely at random (MCAR), an imputation method such as multiple imputation will be considered, recognizing the limitations with these methods due to the small sample size.

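### SAP 5.0 keeps only eligible participants without significant protocol violations, an undefined filter that contradicts the modified intent-to-treat rule stated in its next sentence and elsewhere

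*SAP*

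**What the plan says.** The second paragraph of SAP 5.0 (Study Population) refers to the small size of the study. It then limits the data to participants who satisfied the eligibility criteria and "who were not involved in any significant protocol violations will be used". The sentence directly after it reads: "The intent-to-treat population consists of all randomized participants who receive the first treatment". That sentence mentions neither eligibility nor violations.

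Other sections address the same matter:

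- SAP 4.1.2 gives the same randomised-and-treated definition, and SAP 7.3 and Protocol 7.8.2.2 apply it to the efficacy analyses. In SAP 7.3 these participants "will be included in the analysis and analyzed in the arm to which they were randomized".
- SAP 4.1.4: "No per protocol population is planned for this study".
- SAP 4.3 assigns the safety analyses to the safety population and all others to the ITT population.
- SAP 7.5: "all available data will be used for all analyses".
- Protocol 6.1.6: "Any departure from procedures or requirements outlined in the protocol will be classified as protocol deviations". It has no grade of significant or major.
- SAP 8.2 counts and lists deviations and attaches no exclusion rule to them.

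**The concern.** The restriction in 5.0 works like a per-protocol filter, but it belongs to no analysis set that the SAP defines. Because it depends on events after randomisation, applying it would break the randomised comparison that the modified intent-to-treat rule protects.

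It also cannot be applied as written, since significance has no criteria, no adjudicator, no timing and no masking requirement. SAP 3.4.2 leaves all data coordinating center staff unmasked, and Protocol 6.1.1 gives that center the final analysis, in collaboration with the PI. The text does not authorise exclusions made with knowledge of the arm, but nothing in it prevents them if 5.0 is followed.

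The sentence is not limited to efficacy. Read literally, it would also remove adverse events in participants with violations from the primary safety outcome, although SAP 4.1.3 defines the safety population as everyone who consented.

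**Working it through.** **Which rule governs**

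| Place | Who is included | Violation filter? |
|---|---|---|
| SAP 5.0, restricting sentence | Eligible, no significant violation | Yes, undefined |
| SAP 5.0, next sentence | Randomised and first treatment received | No |
| SAP 4.1.2, SAP 7.3, Protocol 7.8.2.2 | Randomised and first injection received | No |
| SAP 3.6, Table 2 | Those who refuse or cannot have the second treatment stay in ITT | No |
| SAP 4.1.3 | All who consented (safety) | No |
| SAP 4.1.4 | No per-protocol set | No |
| SAP 11.0, outcome tables | ITT | No |

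Only one sentence carries the filter, and no table is assigned to a filtered set. However, SAP 4.3 says that departures from its conventions will be noted in later sub-sections, and 5.0 follows directly. A reader could therefore take the filter as an intended exception.

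**Possible size (illustration)**

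Inputs: 20 participants randomised 1:1 (SAP 3.2, 3.3), taken as 10 per arm. SAP Appendix 13.1 gives a patient-level SD of 15 letters and a measurement-error SD of 6.2. The number of violators is not given, so one exclusion is assumed.

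1. Check that the SDs are read as the SAP uses them. The original-scale SD is √(15² + 6.2²) = 16.23. A two-sided t-test at 0.05 with 10 per arm then has 74.1% power at 20 letters and reaches 70% at 19.1 letters. This agrees with the Appendix statement that power does not approach 70% until the difference is about 20 letters.
2. Shift of the arm mean. If the excluded eye lies d letters below the mean of its nine arm-mates, the arm mean moves by d/10. For d = 10, 20 and 30, that is 1, 2 and 3 letters.
3. Standard error of the arm difference.
   - Change from baseline, assuming independent errors and a patient effect that cancels: SD = 6.2 × √2 = 8.77; SE = 8.77 × √(2/10) = 3.92.
   - Original scale: SE = 16.23 × √(2/10) = 7.26.
4. A 2-letter shift is 2/3.92 = 0.51 SE for change and 2/7.26 = 0.28 SE on the original scale.
5. How unusual is d = 20? For change, the gap between one eye and the mean of nine has SD 8.77 × √(10/9) = 9.2, so 20 letters is about 2.2 SD. If the eye is excluded without regard to outcome and errors are normal, the expected absolute gap is 9.2 × √(2/π) ≈ 7.4 letters. That is a shift of 0.74 letters, or 0.74/3.92 ≈ 0.19 SE. The ratio is the same on the original scale.
6. Precision. With 9 v 10 the SE grows by √(1/9 + 1/10)/√(2/10) = 1.027. With 9 v 9 it grows by √(2/9)/√(2/10) = 1.054. Power at 20 letters falls from 74.1% to 71.5% and 69.0%.

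The loss of precision is small. The concern is selection: an exclusion related to outcome or arm could move the estimate by a material part of a standard error.

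**The case against.** The strongest reply is that this is leftover text. Every operative section uses the randomised-and-treated population, no table is assigned a filtered set, and 5.0 itself ends by restating intent-to-treat. Efficacy is secondary and exploratory, and Protocol 7.8.2.2 rules out using the p-values for hypothesis testing. The eligibility half of the filter should rarely act, because randomisation follows confirmed eligibility. All of this stands, and it makes the harm conditional. It does not say which rule was prespecified, and SAP 10.0 lists this text as the finalised version 1.0.

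Two supporting passages are weaker than the rest. The phrase in SAP 4.3, "regardless of the subsequent sequence of events regarding study drug exposure", concerns the arm in which a participant is analysed; a separate sentence there carries the population rule. SAP 7.5 is a missing-data rule and could be read alongside 5.0. The contradiction does not depend on either.

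The 20-letter illustration is an atypical eye, and the typical figure is nearer 0.2 SE. That is a fair limit on the size.

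The Manual of Procedures and the SAP shells were not available and might define the term. SAP 5.0 cites no definition, and a definition would not remove the conflict with 4.1.2, 4.1.4 and 7.3.

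**Conclusion.** The concern holds. SAP 5.0 states an inclusion rule that cannot stand with its own next sentence or with SAP 4.1.2, 4.1.4, 4.3 and 7.3 and Protocol 7.8.2.2, and its key term is undefined in both documents. This should be corrected, but there is no evidence that any result has been or will be affected.

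If the rule were applied to one participant, the arm difference would move by roughly 0.2 SE for a typical eye and by 0.3 to 0.5 SE for one 20 letters from its arm-mates. These figures assume 10 per arm, the Appendix SDs and a single exclusion; for change from baseline they also assume independent errors.

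**What to change.** In SAP 5.0, delete the words that restrict the data to eligible participants without significant violations. The sentence then says that all available data from the stated analysis sets are used: modified intent-to-treat for efficacy and, as SAP 4.3 has it, the safety population for safety. The table list in SAP 11.0 assigns ITT to the safety tables. That mismatch with 4.3 already exists, and the same revision can reconcile it.

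If an analysis without violators is wanted, name it as a sensitivity analysis and fix its criteria before database lock. Someone masked to arm, for example the masked PI, should apply them to a deviation listing stripped of detail that reveals the arm. This is optional and adds work, because unmasked staff report some of the deviations.

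The required change is one deleted clause. Since version 1.0 is final, it also needs a SAP revision and an entry in the revision history.

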5.1 Eligibility Criteria for Selection of Study Population

5.1.1 Study Eye Inclusion/Exclusion Criteria

Inclusion criteria for the study eye are:

- 1. Clinical diagnosis of central retinal vein occlusion (CRVO) confirmed by review of medical records and screening assessment.
- 2. BCVA obtained during the screening period is in the range of 20/40+ to 20/400- (ETDRS letter score in the range of 18 to 73, inclusive).
- 3. Duration of vision loss from CRVO \geq 6 months to \leq 42 months.

Exclusion criteria for the study eye are:

- 1. Previous eye treatment with intravitreal or periocular steroids, laser or intraocular surgery within 6 months prior to enrollment (i.e., date ICF signed) or treatment is expected to be given during the study period.
- For eyes requiring treatment to prevent recurrent macular edema, on-going intravitreal anti-VEGF treatment is expected to be given at an interval < every 8 weeks during the study period or anti-VEGF therapy was started less than 24 weeks prior to informed consent.
- 3. History or concurrent ocular herpes infection.
- 4. Active non-herpetic eye infection diagnosed within 8 weeks from enrollment (i.e., date ICF signed).
- 5. Glaucoma requiring treatment with more than 2 medications, laser or intraocular surgery.
- 6. Active uveitis or history of recurrent uveitis or uveitis involving the posterior segment.
- 7. Presence of cataract that is impairing vision.
- 8. Presence of lens or lens implant subluxation.
- 9. History of ocular trauma that is currently impairing vision.
- 10. Any concurrent optic nerve or retinal disease that is visually significant or likely to progress to visual significance during the 1-year study follow-up. The excluded eyes include eyes with AREDS category 2 to 3 age-related macular degeneration (AMD) with foveal involvement of drusen or RPE changes, and any AREDS category 4 AMD eyes. For eyes with ERM, the excluded eyes include eyes with OCT evidence of foveal deformation. For optic nerve disease, eyes with any associated visual field deficit or history of associated CNVM are excluded. For glaucoma eyes, eyes requiring glaucoma laser trabeculectomy or glaucoma surgery to maintain IOP are excluded.
- 11. Active retinal or iris neovascularization.
- 12. Macular edema requiring on-going therapy or where such treatment is expected during the study period, with the exception of anti-VEGF treatment given at an interval of 8 weeks or greater.

- 13. Significant media opacity precluding view of the fundus for examination, photography or optical coherence tomography (OCT) including cataract and vitreous haze.
- 14. High myopia (> 9 diopters)
- 15. Amblyopia
- 16. Other cause contributing to vision loss at screening.
- 17. History of any of the following procedures: corneal transplant, glaucoma surgery, or intraocular silicone oil.
- 5.1.2 Participant-Level Inclusion/Exclusion Criteria

Participants must meet the following inclusion criteria:

- 1. Age \geq 18 years of age.
- Female participants of child-bearing potential (see APPENDIX B in protocol for definition) must not be pregnant or breastfeeding and have a negative urine pregnancy test within 14 days prior to sham injection and/or CD34+ cell injection.
- Females of childbearing potential must have had a hysterectomy, be completely abstinent from intercourse or must agree to practice effective contraception for the duration of the study. Acceptable methods of contraception include hormonal contraception, intrauterine device, barrier methods (diaphragm, condom) with spermicide, or surgical sterilization (tubal ligation).
- 4. Able and willing to sign informed consent.
- 5. Able to keep follow-up appointments for at least 12 months as determined by the investigator.

Participants with any of the following criteria will be excluded from the study:

- 1. Concurrent treatment with an investigational drug or device.
- 2. Concurrent use of systemic immunosuppressive therapy or history of use within 3 months prior to enrollment (i.e., date ICF signed).
- 3. Concurrent use of anticoagulation therapy except for aspirin without an acceptable safe stopping plan for study treatments.
- Known history of coagulopathy or other hematologic abnormality that may put participant at risk for bleeding or infection or raise concerns about quality or quantity of CD34+ cells isolated.
- 5. History of allergy to fluorescein dye.
- 6. Participant who has had a prior or concomitant malignancy with the exception of the following: 1) adequately treated basal or squamous cell carcinoma of the skin, or 2) any other malignancy from which the patient has remained disease free for more than five years.
- 7. Current active systemic infection as evidenced by fever greater than 100.4 or any evidence of systemic infection as determined by the study physician.
- 8. Any diagnosis of active infection or vaccination within 8 weeks prior to receipt of study treatment.
- 9. Diabetes mellitus with known systemic complications by self-report or physiciandetermined by medical history or examination.

- 10. History of prior radiotherapy to head/neck area.
- 11. Poorly controlled hypertension with systolic > 180 or diastolic > 95.
- 12. Serious medical or psychiatric condition that, in the opinion of the Investigator, would make study participation hazardous to the participant or compromise study findings or would prevent the participant from completing the study.
- 13. Any physical characteristic that precludes ability to perform study diagnostic testing.

6.0 ANALYSIS OF PARTICIPANT CHARACTERISTICS

Baseline demographics and characteristics such as gender, age, ethnicity, and race will be summarized by treatment group. A summary of baseline medical history data will present the number and percent of participants with each captured condition organized by body system and treatment group. A summary of baseline ocular history data in both the study and fellow eyes will present the number and percent of participants with each captured ocular condition organized by treatment group.

7.0 OUTCOME ANALYSIS

7.1 Primary Outcomes

The primary objective of the study is to assess the safety and feasibility of the stem cell therapy. The primary safety outcome focuses on the participants' adverse event experience during Treatment Period 1, whereas the secondary safety outcome encompasses the AE experience throughout study duration. Section 7.1.1 describes analyses for the primary and secondary safety outcomes and section 7.1.2 describes the feasibility outcome analyses.

